### **9.1.3. Strengths of study design**

The strength of the non-interventional study design is that it allows to observe diverse populations in a broad range of settings (natural environment) reflecting reality. All decisions in terms of diagnostic procedures, treatments, management of the disease and resource utilization are fully dependent on mutual agreement between the patient and the attending physician, without interference by a sponsor or study protocol.

## **9.2. Setting**

### **9.2.1. Eligibility**

Patients enrolled in this study have a diagnosis of unresectable HCC in whom a decision to treat with TACE has been made at time of study enrollment.

### **9.2.2. Inclusion criteria**

- Patients with histologically/cytologically documented or radiographically diagnosed HCC. Radiographic diagnosis needs typical findings of HCC by radiographic method i.e. on multi-dimensional dynamic CT, CT hepatic arteriography (CTHA)/CT arterial portography (CTAP) or MRI.
- Patients with BCLC stage B or higher.
- Patients in whom a decision to treat with TACE has been made at time of study enrollment. Patients that have received one TACE in the past also can be enrolled, if the TACE was done at the same site and all required data about such previous TACEs are available. TACE

includes both conventional TACE with lipiodiol (or similar agents) and chemotherapeutic agent(s) and TACE with DC Beads® excluding TAE without chemotherapeutic agent.

- Patients with unresectable HCC (incurable with curative treatments including resection or ablation or not eligible for resection or local ablation)
- Patients must have signed an informed consent form
- Patients must have a life expectancy of at least 8 weeks

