### **8.2. Secondary objective(s)**

Secondary objectives are:

- To evaluate progression-free survival (PFS), time to progression (TTP), tumor response and AE from time of TACE non-eligibility overall and in the cohorts of special interest
- To evaluate overall survival (OS), progression-free survival (PFS), time to progression (TTP), tumor response and AE from start of sorafenib treatment.
- To determine duration of treatment (DOT) of sorafenib after TACE with respect to the start of sorafenib treatment (early vs. not early).
- To determine time to meet TACE non-eligibility criteria from initial TACE according to the guidelines
- To determine the proportions of patients who receive sorafenib after TACE and those who do not receive sorafenib after TACE, respectively, regionally and globally
- To evaluate response to TACE by number of TACEs
- To evaluate deterioration of liver dysfunction in the course of TACE treatment and thereafter.
- To evaluate OS from initial TACE for all patients in the study irrespective of their treatment after TACE
- To evaluate deviations from recommendations for TACE use in the treatment guidelines for TACE use, regionally and globally
- In addition, practice patterns of the physicians involved in the care of patients with HCC under real-life conditions will be evaluated.

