### **9.2.3. Exclusion criteria**

- Patients who have received TACE in the past but the data about TACE required in this protocol are not available
- Patients who received any systemic anti-cancer therapy prior to the first TACE
- Patients who are treated according to a trial protocol for intervention including a locoregional therapy or systemic therapy
- Hospice patients

All contra-indications according to the local marketing authorization should be considered.

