## **9.4. Data sources**

The investigator collects historic data (demographic and clinical characteristics) from medical records if available. Likewise, the investigator collects treatment related data, results of tumor assessments and other disease status information, also documented in the medical record, during visits that take place in routine practice. For any adverse events that occur, information is directly obtained from the patient. In case a patient is seen by more than one physician for his/her disease (e.g. the patient is monitored by a physician other than the initial investigator), the initial investigator should make every effort to collect information on any visits (including results) that have taken place outside the investigator's site

due to the patient's disease, for example by interviewing the respective physician or patient or by obtaining an accompanying letter with detailed information and results.

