### **10.4. Patient information and consent**

Before documentation of any data, informed consent is obtained by the patient in writing. In countries where required by law or regulation, the investigator must have the IECs/IRB written approval/favorable opinion of the written informed consent form and any other written information to be provided to patients prior to the beginning of the observation.

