## **11.2. Collection**

Starting with the first TACE, all non-serious Adverse Events (AE) must be documented on the AE Report Form or to the electronic CRF within 5 days of awareness. All serious AEs (SAE) must be documented immediately (within 24 hours of awareness).

For each AE/SAE, the investigator must assess and document the seriousness, duration, causal relationship to study drug (TACE/sorafenib/other systemic anti-cancer drug), action taken and outcome of the event.

If a pregnancy occurs during the study, although it is not a serious adverse event, it should be reported within the same time limits as a serious adverse event. The result of a pregnancy should be followed carefully and any abnormal result of the mother or baby should be reported.

The documentation of any AE/SAE ends with the completion of the “End of observation” section of the electronic CRF. However, any AE/SAE occurring up to 30 days after the last intake of Sorafenib has to be documented, even if this period goes beyond the end of observation.

As long as the patient has not received any TACE or any other studied treatment, AEs/SAEs do not need to be documented as such in this non-interventional study. However, they are part of the patient’s medical history.

For any serious drug-related AE occurring after study end, the standard procedures that are in place for spontaneous reporting have to be followed.

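### First-TACE results pool patients enrolled before TACE 1 with patients enrolled after it, whose TACE 1 counts only if they survived to consent, had complete data and were again due for TACE

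*Protocol*

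**What the plan says.** **Entry.** Section 9.2.1 describes enrolled patients as those "in whom a decision to treat with TACE has been made at time of study enrollment". Section 9.2.2 adds: "Patients that have received one TACE in the past also can be enrolled, if the TACE was done at the same site", on the further condition that "all required data about such previous TACEs are available". Section 9.2.3 excludes "Patients who have received TACE in the past but the data about TACE required in this protocol are not available". Section 10.4 states: "Before documentation of any data, informed consent is obtained by the patient in writing". Section 9.2.5 foresees that the first TACE of such a patient, and the initial-visit baseline, are documented retrospectively.

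**Use of the data.** A secondary objective in 8.2 is "To evaluate response to TACE by number of TACEs". Section 9.3.9 has response recorded for every TACE. Section 9.7.5 defines the Overall set as everyone with at least one TACE. Section 9.7.7 summarises response to each TACE and liver deterioration in that set. Liver deterioration, as defined in 9.1.2, includes liver-related AEs and worsening up to Grade 5. Section 9.7.6 summarises AEs overall, by cohort, by grade and by type of HCC treatment.

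**AE collection.** Section 11.2 states: "Starting with the first TACE, all non-serious Adverse Events (AE) must be documented", within 5 days of awareness, or 24 hours if serious. It makes no exception for a TACE given before consent. Section 9.4 states: "For any adverse events that occur, information is directly obtained from the patient". Table 2 lists AEs at follow-up and last visits only.

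**How the protocol presents the design.** Section 7 names prospective TACE documentation as the advance over the sponsor's previous observational study. Section 9.2.4 relies on consecutive enrolment against selection bias. Section 9.8.4 mentions selection bias in general terms but not this entry route. No limit is set on the share of late entrants or on the time since their first TACE.

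**The concern.** A patient enrolled before TACE 1 contributes that TACE whatever follows: death, decompensation, complete response with no further TACE, or re-treatment. A late entrant contributes TACE 1 only after its early outcome is known and only if that outcome was compatible with consent and a further TACE decision. The entry rule thus selects on the outcome being summarised, and it does so for TACE 1 alone. Any TACE given in the study is counted regardless of what happens next.

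At stake is a stated secondary result. When response is tabulated by TACE number, the TACE 1 row blends an unselected and a selected group in proportions the protocol does not control. A difference between that row and later rows may then partly reflect how patients entered. Summaries of TACE-related AEs and liver deterioration lack the fatal outcomes that kept some patients from ever being enrolled.

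**Working it through.** **The plan's own figure.** This point rests on no figure in the protocol. The main design figure is the 83% power in 9.5, and it reproduces. Medians of 12 and 9 months, 18 months' uniform accrual and 36 months' total duration give event probabilities of 0.780 and 0.865. With 250 per cohort that is 250 × (0.780 + 0.865) ≈ 411 events. Power = Φ(½ × √411.2 × |ln 0.75| − 1.960) = Φ(0.957) = 83.1%. Late entry does not touch it.

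**Inputs that must be assumed.** The protocol gives neither the late-entrant share f nor any response, fatality or re-treatment rate. I take f = 10%, 30% and 50%, and the same true rates at every TACE and in both entry groups.

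**Fatal outcomes.** Let d be the true fatal rate of a TACE before the next treatment decision. If all such deaths would precede consent, late entrants contribute none, so the recorded TACE 1 rate is (1 − f) × d. With d = 4%:
- f = 10%: 0.9 × 4% = 3.6%
- f = 30%: 0.7 × 4% = 2.8%
- f = 50%: 0.5 × 4% = 2.0%

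TACEs given in the study keep 4%. If some of these deaths would fall after consent, the shortfall is smaller.

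**Response.** Let R be the true response rate, and q_R and q_N the chances that responders and non-responders are chosen for another TACE. Among late entrants, response is R_L = R·q_R / [R·q_R + (1 − R)·q_N]. The pooled TACE 1 rate is (1 − f)·R + f·R_L. With R = 50%:

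| q_R / q_N | R_L | f = 10% | f = 30% | f = 50% |
|---|---|---|---|---|
| 0.40 / 0.70 | 36.4% | 48.6% | 45.9% | 43.2% |
| 0.60 / 0.60 | 50.0% | 50.0% | 50.0% | 50.0% |
| 0.70 / 0.40 | 63.6% | 51.4% | 54.1% | 56.8% |

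The shift is −1.4 to −6.8 points, zero, or +1.4 to +6.8 points.

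**Complete response as a special case.** Take a true rate of 30%, with re-treatment of 30% of complete responders against 70% of the others. Then R_L = 0.09 / (0.09 + 0.49) = 15.5%, and the pooled rates are 28.6%, 25.7% and 22.8% for f = 10%, 30% and 50%. With 50% of complete responders re-treated, R_L = 0.15 / (0.15 + 0.49) = 23.4%, and the pooled rates are 29.3%, 28.0% and 26.7%. These fall below 30% only because complete responders are assumed to be re-treated less often.

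**AE timing, side by side.** Section 11.2 starts AE documentation at the first TACE and sets 5-day and 24-hour limits. Section 9.2.5 lets that TACE precede consent, and 10.4 bars documentation before consent. The limits cannot work as prospective collection for such a TACE, and Table 2 gives the initial visit no AE entry. The protocol does not say which rule applies.

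**The case against.** The strongest reply is that most of the alarming consequences are not in the document. Several readings are tempting and do not stand:

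- *First-TACE response is understated.* The entry rule removes complete responders who need no more TACE, which lowers the rate. It also removes patients who decompensate or die, which raises it. The direction cannot be fixed from the protocol.
- *The change from TACE 1 to TACE 2 is the objective, and AEs will seem to rise with repeated TACE.* Section 8.2 asks only for response by number of TACEs. No such contrast and no AE table by TACE number is planned. In 9.7.7, the phrase about procedures of TACE may refer to technique rather than number.
- *AEs of the earlier TACE are collected by recall, and the not-evaluable category is suppressed.* The TACE must have been done at the same site with its data available, and historic data come from medical records. The sentence in 9.4 does not say that recall is used for a TACE before enrolment. Not evaluable is itself a valid recorded response.
- *Results from TACE 2 onward are clean.* Under any enrolment rule, patients with a second TACE are survivors chosen for re-treatment. Unpaired rows by TACE number always compare different populations.

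It can also be said that 9.2.2 might be read as an entry route without a TACE decision, although 9.2.1 describes all enrolled patients. Finally, a separate display of retrospectively documented TACE 1 could be in the SAP, which is not shown.

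These replies limit the point but do not remove it. Survival to consent and available data are conditions on late entrants under either reading of 9.2.2. The protocol itself fixes the entry route, the pooled analysis set and the start of AE collection.

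**Conclusion.** The point holds in a limited form. Pooled TACE 1 data mix a group observed regardless of outcome with a group selected on early outcome, while TACEs given in the study carry no such selection on their own result.

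Only one direction is certain: late entrants can contribute no death between TACE 1 and consent, so fatal outcomes of TACE 1 are under-recorded. On the assumptions above, 4% becomes 3.6% at a 10% share and 2.0% at 50%. Response may move by up to 6.8 points either way at a 50% share, or not at all. These are illustrations, because the share of late entrants and the re-treatment pattern are unknown. In an AE summary pooled over all TACEs, later TACEs dilute the effect.

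The consequence is confined to descriptive secondary and safety summaries. The primary clock starts at TACE non-eligibility or, where that already exists, at enrolment (9.1.1), so the primary endpoint is not the target.

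**What to change.** In 9.7.5 and 9.7.7, state that:

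1. The main TACE 1 estimates of response, liver deterioration and TACE-related AEs use only patients enrolled before TACE 1.
2. Patients enrolled after one TACE contribute from their first TACE after enrolment, keeping its true sequence number.
3. Their retrospectively documented TACE 1 is shown separately, with the number of such patients.
4. Any within-patient comparison of TACE 1 and TACE 2 among patients who received both keeps their TACE 1. There they meet the same condition as everyone else, and dropping them would discard valid pairs.

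Reconcile 11.2 with 9.2.5: say whether and from what source AEs of a TACE before enrolment are documented, and how the time limits apply to them.

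The cost is one population rule and a short clarification. TACE dates are recorded under 9.3.10, and the enrolment date is already needed for 9.1.1. The downside is fewer patients in the main first-TACE summary. The rule does not make unpaired results at different TACE numbers comparable, since re-treated patients remain a selected group, and the report should say so.

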### **9.2.3. Exclusion criteria**

- Patients who have received TACE in the past but the data about TACE required in this protocol are not available
- Patients who received any systemic anti-cancer therapy prior to the first TACE
- Patients who are treated according to a trial protocol for intervention including a locoregional therapy or systemic therapy
- Hospice patients

All contra-indications according to the local marketing authorization should be considered.

### **9.2.4. Representativeness**

No further selection than outlined in Section 9.2.1-9.2.3 should be made and patients should be enrolled consecutively in order to avoid any selection bias and thus to increase the likelihood of representativeness.

### **9.2.5. Visits**

The start of the study is the date from which information on the first study subject can be first recorded in the study dataset. The end of the study is date after which the last enrolled subject will have been in the study for 18 months, or is lost to follow-up or has died.

The investigator documents an initial, follow-up visits and a final visit for each patient in the case report form (CRF). After the initial visit at least one follow-up visit should be documented. A certain number or frequency of visits is not requested by this protocol. Documentation follows the actual clinical practice. A visit is defined as any status assessment or new treatment decision the treating physician takes with the presence of the patient. The time interval between two documented status assessments is assumed to be 6 - 12 weeks, although this will be at the treating physician's discretion.

In the case that the first TACE is documented retrospectively under the pre-requisites detailed in section 9.2.2. the baseline data asked in the initial visit also has to be documented retrospectively.

The final data collection (last visit) is at patient's death or at end of study (whatever is earlier). If the documentation is stopped prematurely, the reasons for the end of observation have to be given. If a patient will join an interventional clinical study during the course of observation, at least the information on survival will still be collected up to the end of this study.

The observation period for each patient is estimated to be about 18 months and covers the period from first TACE to death. If a patient will still be alive at time of study closure, this will be documented in the final visit.

The CRF is available upon request. The respective document is listed in Annex 1.

### 9.3. Variables

The investigator collects historic data (demographic and clinical characteristics) from medical records if available, or else by interviewing the patient. Likewise, the investigator collects treatment related data during initial visit and follow-up visits.

Table 2: Tabulated overview on variables collected during the study

	Study Entry/ Initial visit	Follow-up visit	Last visit / End of observation
patient information and consent	X		
specialty of the investigator and previous physician(s)	X		
demographic data	X		
Current alcohol consumption	X		
etiology of underlying disease/findings	X		
past medical history and concomitant diseases	X		
date of initial HCC diagnosis	X		
Disease status at initial diagnosis (BCLC stage, TNM classification)	X		
previous treatments for HCC	X		
height	X		
smoking	X		
alcohol use	X		
visit date	X	X	X
blood pressure	X	X	
body weight	X	X	
Disease status (BCLC stage, TNM classification)	X	X	
Child-Pugh score	X	X	
performance status (ECOG)	X	X	
Tumor assessment *	X	X	
response evaluation compared to initial TACE		X	
response evaluation compared to most recent TACE		X	
response evaluation compared to initiation of sorafenib		X	
laboratory data	X	X	
Decision on further treatment**		X	
Details on TACE treatment (date, embolization agent, drug name)		X	
Details on sorafenib therapy (dates, daily dose, interruptions)		X	
Details on other systemic therapy for HCC		X	
Disease status summary**	X	X	
AE		X	X
concomitant medication (including non-systemic therapy for HCC)	X	X	X
Reasons for end of observation			X
physician's signature			X (one signature at the end of documentation)

\* The time interval between two documented tumor assessments is assumed to be 6 - 12 weeks, although this will be at the treating physician's discretion

\*\* Must be documented at each follow-up visit

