Study size	In order to achieve 1,500 completely documented patients, approximately 1670 patients will be enrolled assuming a 10% loss to follow-up rate.
Data analysis	
STATISTICAL CONSIDERATIONS:
 
In general, statistical analyses will be of explorative and descriptive nature.
 
Analyses will be performed for the total study population (overall analysis) and separately for the two patient cohorts of special interest, as appropriate.
 
The primary efficacy endpoint is Overall Survival (OS). It is defined in this study as the time period from documented TACE non-eligibility to death due to any cause.
 
For the two cohorts of special interest, Kaplan-Meier (KM) estimates for OS will be displayed. Furthermore, these two cohorts will be compared regarding overall survival using a Cox proportional hazards model.
 
In order to cope with confounding typically present in non-randomized studies a stratified propensity score approach will be applied. The propensity score model will be determined in an outcome-blinded manner including variables potentially affecting the treatment decision at time of TACE non-eligibility as well as known confounders. Based on the resulting propensity scores, equally sized strata will be determined and within each stratum the stratum-specific hazard ratio will be estimated. Subsequently, an overall hazard ratio estimate as well as the corresponding 95% confidence interval will be determined based on the stratum-specific estimates.
 
Where applicable, the same propensity score approach will be applied in order to compare the two cohorts regarding secondary endpoints.
 
It is planned to have the first interim analysis after 500 patients observed for at least 6 months. Based on results of the 1st interim analysis, the second interim analysis is planned after approximately 1000 patients have been observed for at least 6 months, in order to evaluate patient sample size and feasibility for conducting the propensity score analysis. The final analysis will be performed after end of the study, which is the date after which the last enrolled subject will have been in the study for 18

	months, or is lost to follow-up or has died.
Milestones	First patient first visit: Q3 2013 Last patient first visit: Q4 2015 Last patient last visit: Q2 2017 End of data collection (clean database) Q3 2017 Final report of study results: Q1 2018

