- Progression-free survival (PFS) from initiation of sorafenib is defined as the time interval measured from the start date of sorafenib treatment to documented (radiological or clinical) progression or death, whichever comes first.
- Time to progression (TTP) from initiation of sorafenib is defined as the time interval from start date of sorafenib treatment to the date of documented progression. Patients without tumor progression at the end of the study will be censored at their last date of tumor evaluation.
- Duration of sorafenib treatment is defined as the time interval from start date of sorafenib treatment to the date of permanent discontinuation of sorafenib treatment (regardless of the reason for discontinuation including death).
- The tumor status at different visits response according to mRECIST will be evaluated according to the categories “Complete Response”, “Partial Response”, “Stable Disease”, “Clinical Progression”, “Radiological Progression”, and “Not evaluable at this visit”. The best overall response will be analyzed providing absolute and relative frequencies of the tumor status categories.
- Incidence of Treatment-emergent Adverse Events (TEAEs) – patients will be monitored for TEAEs using the NCI-CTCAE Version 4.03. Details on the collection, management and reporting of TEAEs can be found in section 11.

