### **9.3.8. Disease status summary**

The following criteria will be assessed at initial visit and every follow-up visit:

- lack of portal blood flow (because of portal vein thrombosis, portosystemic anastomoses or hepatofugal flow)
- Patients with lobar or segmental portal vein thrombosis.
- Patients with advanced liver disease (Child–Pugh class B or C)
- Clinical symptoms of end-stage cancer
- Extrahepatic spread (N1, M1)
- ECOG PS  $\geq 1$
- BCLC C or D
- Vascular invasion.
- Two or more consecutive incomplete necrosis (depositions (50%) of lipiodol) are seen by response evaluation CT within the treated tumors at the 4 weeks after adequately performed TACE. (excluded from initial visit)
- Two or more consecutive appearances of a new lesion (recurrence) are seen in the liver by response evaluation CT at the 4 weeks after adequately performed TACE. (excluded from initial visit)
- TACE failure by investigator’s assessment (excluded from initial visit)
- Clinical encephalopathy
- Refractory ascites
- Hepatorenal syndrome
- Extensive tumor with massive replacement of both entire lobes
- Technical contraindications to hepatic intra-arterial treatment
- Renal insufficiency (creatinine  $\geq 2$  mg/dL or CrCl  $< 30$  mL/min)
- Other (to be specified)

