### **9.3.9. Tumor assessment**

Patients will be assessed for response to TACE and tumor assessment preferably by mRECIST. In case that an assessment by mRECIST is not possible, because this is not routinely done at the site of the treating physician, also other evaluation criteria can be used. In any case the criteria used have to be documented along with the tumor evaluation and the physician should use the same criteria throughout all tumor evaluations of one patient.

TACE response to most recent TACE will be assessed within 12 weeks after TACE and recorded for each TACE.

Response evaluation will also be done compared to initial TACE. For patients treated with sorafenib, response evaluation compared to initiation of sorafenib will be added.

Tumor assessment will be made at physicians' discretion using CT scan or MRI or equivalent imaging exam, starting from initial TACE.

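### The cohort comparison of PFS and TTP is open to bias from unequal tumor-assessment timing, which a propensity score fixed at TACE non-eligibility cannot correct

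*Protocol*

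**What the plan says.** **Event date.** Section 9.1.2 defines TTP for sorafenib-treated patients as "the time interval from start date of sorafenib treatment to the date of documented progression". The definition from first TACE ends the same way. PFS adds death, and its progression may be radiological or clinical. TTP without progression is censored at the last tumor evaluation. Annex 4 dates a new lesion at its first detection on imaging.

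**Assessment timing.** Section 9.2.5 states "A certain number or frequency of visits is not requested by this protocol". The Table 2 footnote in section 9.3 says "The time interval between two documented tumor assessments is assumed to be 6 - 12 weeks" and leaves the interval to the treating physician. Section 9.3.9 says "Tumor assessment will be made at physicians' discretion using CT scan or MRI or equivalent imaging exam, starting from initial TACE".

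**Link to treatment.** Section 9.3.9 also says "TACE response to most recent TACE will be assessed within 12 weeks after TACE and recorded for each TACE". Two of the non-eligibility criteria in section 9.3.8 rest on a CT timed at 4 weeks after TACE; one describes findings that "are seen by response evaluation CT within the treated tumors at the 4 weeks after adequately performed TACE". For sorafenib, section 9.3.9 adds a response evaluation against the start of the drug, and Table 2 lists it for follow-up visits, but neither gives a window.

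**Comparison.** Section 8.2 asks for PFS and TTP from TACE non-eligibility in the two cohorts. The abstract adds that, where applicable, "the same propensity score approach will be applied in order to compare the two cohorts regarding secondary endpoints". Section 9.7.4 describes that approach as stratum-specific Cox hazard ratios pooled by inverse variance.

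**The concern.** A progression found by imaging is recorded at the assessment that finds it, so its recorded date is late by the time since it occurred. On average that is about half the assessment interval. If one cohort is assessed less often, its progressions are recorded later and its PFS and TTP look longer even when the true hazards are equal.

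The cohorts are defined by the treatment chosen at TACE non-eligibility, and assessment timing is partly tied to treatment, so unequal intervals are plausible. The propensity score balances variables known at that moment. It does nothing about imaging frequency afterwards.

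Sections 9.7.8 and 9.8.4 discuss confounding, channeling and selection, but not assessment timing. Annex 2 (item 7.1.2) nevertheless ticks information bias as addressed. Without the intervals, a reader cannot tell whether a PFS or TTP difference reflects treatment or timing of assessment.

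**Working it through.** **The plan's own figure.** The only power figure is for OS (section 9.5): medians 9 and 12 months, 250 per cohort, 18 months' accrual, 36 months in total, one-sided 2.5%.
- P(event) = 1 − (e^(−18λ) − e^(−36λ)) / (18λ), with λ = ln 2 / median. This gives 0.780 (12 months) and 0.865 (9 months).
- Events = 250 × (0.7802 + 0.8647) = 411.
- Power = Φ(√411 × |ln 0.75| / 2 − 1.96) = 83.1%, against 83% stated. It reproduces.

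There is no corresponding figure for PFS or TTP, so the size has to be illustrated under assumptions.

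**Hand check, 12 versus 6 weeks.** The mean delays are 12/2 = 6 and 6/2 = 3 weeks. With exponential TTP the mean is median / 0.693. The ratio of observed means, more often over less often assessed, approximates the spurious hazard ratio:
- 3 months (13 weeks): mean 18.8; (18.8 + 3) / (18.8 + 6) = 0.88
- 4 months (17.3 weeks): mean 25.0; 28.0 / 31.0 = 0.90
- 6 months (26 weeks): mean 37.5; 40.5 / 43.5 = 0.93

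**Simulation of TTP, true hazard ratio 1.** From the protocol: 250 per cohort, 18 months of observation, intervals within 6-12 weeks. Assumed: exponential TTP with median 3, 4 or 6 months, spacing varied by ±15%, no deaths, and 0% or 30% of progressions detected clinically at their true time. There were 1,000 runs per setting, analyzed with a one-covariate Cox model. Cells give the hazard ratio (less / more often assessed) and, in parentheses, how often the 95% confidence interval excludes 1.

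| Interval (weeks), detection | 3 months | 4 months | 6 months |
|---|---|---|---|
| 6 vs 6, imaging only | 1.00 (4.7%) | 1.00 (5.0%) | 1.00 (5.7%) |
| 9 vs 6, imaging only | 0.91 (17.8%) | 0.94 (10.6%) | 0.97 (5.1%) |
| 12 vs 9, imaging only | 0.88 (27.0%) | 0.92 (14.5%) | 0.96 (7.5%) |
| 12 vs 6, imaging only | 0.84 (47.0%) | 0.89 (25.2%) | 0.94 (10.9%) |
| 12 vs 6, 30% clinical | 0.89 (27.7%) | 0.92 (17.1%) | 0.96 (6.5%) |

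**PFS and mixed cohorts, 12 versus 6 weeks** (true median TTP 3 / 4 / 6 months):
- Deaths added (assumed median 9 months): 0.87 / 0.90 / 0.93. Deaths alone change little.
- Deaths plus 30% clinical detection: 0.90 / 0.92 / 0.95.
- Deaths (assumed median 10.5 months), 30% clinical detection, and only half of cohort 2 on the shorter interval: 0.95 / 0.96 / 0.975.

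**Does the remedy work?** On simulated dates of this kind, an interval-censored model returns a hazard ratio of about 1.00 at 12 versus 6 weeks.

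**The case against.** A reader might infer that TACE brings scans and sorafenib does not, so that cohort 2 is assessed more often and the comparison is biased in favor of early sorafenib. The protocol does not support that.
- Sorafenib does have a response evaluation; it lacks only a window. The 6-12 week footnote covers every patient.
- The within-12-weeks rule after TACE is compatible with that footnote and need not add a scan. The 4-week CT is wording inside two non-eligibility criteria, not an imaging schedule.
- Section 9.7.4 lets cohort 1 continue TACE. Cohort 2 includes patients on other systemic treatment and patients who start sorafenib later. No share is given for those who go on with TACE, so the direction could reverse.

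The 12 versus 6 week setting also puts each whole cohort at opposite ends of the range, which is a worst case. The abstract calls the analyses explorative and descriptive, Annex 2 says the study does not test hypotheses, and no test of PFS or TTP is specified. Statistical detail is deferred to the SAP.

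All of this stands, and it limits the claim to a risk. It does not remove the risk. The protocol itself fixes the event date, the TTP censoring rule and the comparison method, and it reports hazard ratios with 95% confidence intervals. An unknown direction is itself a reason to show the intervals by cohort. If the SAP already provides the analysis proposed below, the point is met.

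**Conclusion.** The planned cohort comparison of PFS and TTP is open to bias toward whichever cohort is assessed less often, and the propensity score cannot correct it. Neither the direction nor the size can be read from the protocol. If actual intervals are similar, the bias is negligible.

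With no true difference, the spurious TTP hazard ratio is 0.84-0.94 at 12 versus 6 weeks and 0.91-0.97 at 9 versus 6 weeks. It is nearer 1 when some progressions are detected clinically or when the cohorts mix treatments. These figures rest on assumed exponential TTP with a median of 3 to 6 months and on assumed intervals. They also assume that the documented-progression rule in section 9.1.2 carries over to PFS and TTP measured from TACE non-eligibility.

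Primary OS does not depend on the assessment date and is unaffected. The point concerns explorative secondary endpoints, but the correction is cheap enough to be worth making.

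**What to change.** 1. Keep the analysis by documented date as defined.
2. Report the distribution of tumor-assessment intervals by cohort, from TACE non-eligibility onward.
3. Prespecify an interval-censored sensitivity analysis of PFS and TTP, stratified by propensity score. Imaging-detected progression lies between the last progression-free assessment and the one that documents it. Deaths (in PFS) and clinically dated progressions keep their dates.
4. State that a cohort difference in PFS or TTP will be interpreted only if it holds in that analysis.

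The cost is one more model on data that Table 2 already collects (visit dates and tumor assessments). Visits, imaging and treatment do not change. The confidence intervals will be slightly wider. The model assumes that assessments are not prompted by progression itself. In routine care some may be, so that assumption should be stated with the result.
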